14.5 Sample Size

A total of 8 participants (2 in dosing cohort 1 and 6 in dosing cohort 2) will contribute to the analysis, with 8 or 25 timepoint measures, respectively. The within-individual variability will be reduced by repeated measurements post-dose. Based on existing data from our study population regarding the percent CD38+HLA-DR+ CD4+ T cells (standard deviation of 4.9%) in our study population and a paired, one sample, repeated measures analysis, we will have greater than 80% power to detect a 2.7% change in CD4+ T cell activation levels post-dose. Similarly, we will have greater than 80% power to detect a 17% change in cell-associated HIV-1 RNA and a 0.37% change in plasma HIV-1 RNA.

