STATISTICS Primary Analysis Plan	[name] has expertise in epidemiology and biostatistics. She will be performing the data analysis for the study. Paired analyses using Wilcoxon signed rank tests will be performed to evaluate whether there is a statistically significant change in markers of immune activation (CD69, CD38, and/or HLA-DR) on CD4+ and CD8+ T cells after a 1 or 3 doses of Euphorbia kansui extract powder prepared as tea. Multivariate analyses will then be performed to evaluate the association between kansui and measures of immune activation at post-dosing, using linear mixed effects models, which account for within-participant correlation of observations and allows for greater stability in the estimate of the outcome measures within individuals. Similarly, for measures of the HIV reservoir, we will perform negative binomial mixed effects regression (a method to analyze over-dispersed count data) to compare the size of the latent HIV reservoir before and after kansui administration.
Rationale for Number of Participants	A total of 8 participants (2 from dosing cohort 1 and 6 from dosing cohort 2) will contribute to the analysis, with 8 or 25 timepoint measures, respectively. The within-individual variability will be reduced by use of the within-individual control measures, as well as the repeated measurements post-dosing. The primary outcome of the study will be an increase in the % T cell activation (CD38+ HLA-DR+) of CD8+ and CD4+ T cells. Based on our recent experience performing a phase 1 trial of canakinumab (an interleukin-1 beta inhibitor) to reduce inflammation in chronic HIV-infected ART-suppressed individuals, ¹ we estimate that we will have 80% power to detect a within-individual increase of 2.7 points in the % CD8+ T cell activation (standard deviation [SD] at 31 days of 1.6%). We will also assess virologic changes as secondary outcomes in the study. Based on data from our recent HIV latency phase 2b trial of disulfiram, ² we estimate that we will have 80% power to detect 0.6-0.7 log increases in cell-associated unsPLICED (CA-US) HIV RNA (SD=0.4 and 0.5 for Day 4 and Day 31, respectively), and a 0.6-0.5 log increases in ultra-sensitive plasma HIV RNA (SD=0.4 and 0.3 for Day 4 and Day 31, respectively).

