1 BACKGROUND

The key challenge of HIV eradication strategies is persistence of a small pool of resting memory CD4+ T cells that harbor latent replication-competent HIV, untouched by current antiretroviral therapy (ART).³ One potential strategy to eliminate this reservoir is a “shock and kill” approach in which agents designed to reverse latency (latency reactivating agents, LRAs) are used to “shock” the virus out of these cells in order for the host immune response, ART, and/or additional immunomodulatory agents can then eliminate virus-expressing cells.⁴⁻⁷ The goal of the current proposal is to evaluate the *in vivo* biological response to an herbal supplement used in traditional Chinese medicine (“kansui”) that has potent *in vitro* latency reactivating capabilities.

Kansui has been prescribed in Chinese medicine for thousands of years as a cathartic agent. It is typically given as a single dose of 0.5 -1.5 grams, and is used to treat intestinal obstruction, nodular skin lesions, water retention, and epilepsy.^{8,9} Kansui extract is made from the *Euphorbia* root and is thought to contain several potentially biologically active components, including a large number of ingenols, which are known to activate and/or interrupt a number of cellular pathways, including some known to be involved in the maintenance of HIV latency.¹⁰⁻¹² Recently, a semi-synthetic version of ingenol from *Euphorbia tirucalli* has been developed as Ing B (Ing B).¹³ Ing B demonstrates the potent ability to reactivate latent HIV in *ex vivo* and non-human primate models.^{11,12,14} Ing B was shown to induce significant immune activation (upregulation of CD38, HLA-DR, CD69 expression on CD4+ T cells) and reactivate virus in both untreated and ART-suppressed SIVmac251-infected rhesus macaques without hypercytokinemia.^{14,15} These effects were observed as early as three days in untreated monkeys¹⁵ to approximately 30 days post-Ing B in ART-suppressed monkeys.¹⁴ The ability to induce T cell activation and viral reactivation were even more pronounced when Ing B was administered concomitantly with another LRA called suberanilohydroxamic acid (SAHA).¹⁴

Kansui contains ingenols that induce immune activation and reactivate latent HIV-1

[figure not shown]

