14 STATISTICAL METHODS AND CONSIDERATIONS

14.1 Data Sets Analyzed

[name] will be performing the data analysis for the study. Paired analyses using Wilcoxon signed rank tests will be performed to evaluate whether there is a statistically significant change in markers of immune activation (CD69, CD38, and/or HLA-DR) on CD4+ and CD8+ T cells after a 1, 2, or 3 doses of *Euphorbia kansui* extract powder prepared as tea compared to baseline (reference will be the average of the three baseline measures). Multivariate analyses will then be performed to evaluate the association between kansui and measures of immune activation at post-dosing, using linear mixed effects models, which account for within-participant correlation of observations and allows for greater stability in the estimate of the outcome measures within individuals. Similarly, for measures of the HIV reservoir, we will perform linear mixed effects regression to compare CA-US RNA levels before and after kansui and use negative binomial mixed effects regression (a method to analyze over-dispersed count data) to compare plasma HIV RNA levels before and after kansui administration (reference will be the average of three baseline measures).

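### The >80% power in Section 14.5 for a 2.7% change in CD4+ activation does not follow from the stated SD of 4.9% and 8 participants without inputs the plan never gives

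*Combined protocol and SAP*

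**What the plan says.** Section 14.5 sizes CD4+ activation from the "percent CD38+HLA-DR+ CD4+ T cells (standard deviation of 4.9%) in our study population" and "a paired, one sample, repeated measures analysis", and concludes that "we will have greater than 80% power to detect a 2.7% change in CD4+ T cell activation levels post-dose". On numbers it says: "A total of 8 participants (2 in dosing cohort 1 and 6 in dosing cohort 2) will contribute to the analysis, with 8 or 25" timepoints per participant. On variance it says only this: "The within-individual variability will be reduced by repeated measurements post-dose".

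Sections 14.1 and 14.4 plan Wilcoxon signed rank tests for within-person change, then linear mixed models. In both, the pre-treatment value is a mean: "reference will be the average of the three baseline measures".

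The synopsis (Rationale for Number of Participants) makes a separate statement for CD8+ cells, based on an earlier canakinumab trial: 80% power for a within-person increase "of 2.7 points in the % CD8+ T cell activation (standard deviation [SD] at 31 days of 1.6"%.

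Neither place gives alpha or sidedness, says whether the SD is that of a level or of a change, or gives a within-person correlation.

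**The concern.** A 2.7-point change against an SD of 4.9 is a standardised effect of 0.55. With six to eight pairs, an effect of that size is ordinarily well short of 80% power. Something else has to supply the difference. Section 14.5 points to repeated measurement but attaches no figure to it.

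The formal primary endpoint is safety, and Section 5.1 says there is no primary efficacy endpoint, so the safety conclusions are not touched. However, the synopsis also calls an increase in CD8+ and CD4+ activation the primary outcome, and this is the only immunologic power statement in Section 14. If the CD4+ result is null, the sentence invites the reading that a 2.7-point change has been excluded, and the stated inputs do not show that the trial could detect one.

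**Working it through.** **Inputs.** Change 2.7, taken as percentage points (14.5 does not say absolute or relative); SD 4.9; n=8 in all, or n=6 for the three-dose cohort (14.5); three baseline values averaged (14.1). Assumed: two-sided 5%, normal data and, in step 3, compound symmetry.

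**1. The plan's figure, with 4.9 as the SD of the paired change.** d = 2.7/4.9 = 0.551. Power comes from the noncentral t with n−1 degrees of freedom and noncentrality d√n.

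- n=8: noncentrality 0.551 × √8 = 1.56, power 27.1%.
- n=6: noncentrality 0.551 × √6 = 1.35, power 19.7%.
- One-sided 5%: 40.6% and 31.7%.
- Normal approximation, two-sided: 34.4% and 27.1%.
- Exact two-sided Wilcoxon signed rank, by simulation: about 23% and 13%.

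None of these reaches 80%. On the two-sided t-test, 80% would take 28 participants.

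**2. Detectable change at 80% power on that reading.**

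- t-test: d = 1.156 (n=8) or 1.435 (n=6). Multiplied by 4.9, this is 5.7 or 7.0 points.
- Wilcoxon: d of about 1.25 or 1.80, which is about 6.1 or 8.8 points. The t-test multipliers are too small here: under the Wilcoxon test they give only about 74% and 62% power.

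Turned round, 80% power for 2.7 points by t-test needs an SD of the change of at most 2.7/1.156 = 2.34 (n=8) or 2.7/1.435 = 1.88 (n=6).

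**3. With 4.9 as the SD of a single measurement.** For three baselines and m averaged post-dose values,

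SD of change = 4.9 × √[(1 − ρ)(1/3 + 1/m)],

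so 80% power needs ρ ≥ 1 − (SDmax/4.9)² / (1/3 + 1/m), where SDmax is 2.34 or 1.88. Here (2.336/4.9)² = 0.227 and (1.882/4.9)² = 0.1475.

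| Post-dose values averaged | ρ needed, n=8 | ρ needed, n=6 |
|---|---|---|
| 1 | 0.83 | 0.89 |
| 5 | 0.57 | 0.72 |
| 10 | 0.48 | 0.66 |

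For a single post-dose visit, power at ρ = 0.5 is 38% (n=8) or 27% (n=6), and at ρ = 0.7 it is 56% or 41%. For five averaged values it is 74% or 56%, and 91% or 77%.

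The table assumes that every averaged sample carries the full 2.7 points. In the Study Events Tables, Cohort 1 has five post-dose samples and each Cohort 2 phase has ten, so the ten-value row is optimistic for all eight participants together.

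**4. The synopsis CD8+ figure.** With 1.6 as the SD of change, d = 2.7/1.6 = 1.69, and power is 98.2% (n=8) or 90.5% (n=6), not 80%. Two readings give about 80%: n=5 (80.2%), or n=8 with 1.6 as a single-measurement SD and zero correlation (SD of change 1.6 × √2 = 2.26, power 82.4%). The synopsis states neither.

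**The case against.** The strongest defence is that 14.5 does not present 4.9% as the SD of a change. It is the SD of a percentage in the study population, which reads more naturally as the SD of a level, and the analysis is described as repeated measures. On that reading, step 3 shows that 80% can be reached at correlations that are not extreme once several samples are averaged. This stands. A reader might infer from step 1 that true power is 20–27%, but the documents do not establish that, because it depends on a reading of the SD that they leave open.

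A reader might also infer that the synopsis contradicts 14.5, since 2.7 appears with SDs about threefold apart. The documents do not support that. The synopsis figure is for CD8+ cells at 31 days, from another trial; the 14.5 figure is for CD4+ cells. For the same reason, scaling one by the other (2.7 × 4.9/1.6 = 8.3 points) mixes two markers. Nor does the synopsis need an SD as small as 1.6 for 80% power, since step 2 allows up to 2.34 or 1.88.

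Finally, one might argue that averaging cannot help because most Cohort 2 samples in a phase (8 of 10) precede 72 hours, while the Background says "These effects were observed as early as three days in untreated monkeys". That sentence concerns Ing B, a semi-synthetic ingenol, in SIV-infected macaques. It gives no onset time for oral kansui in people, so it cannot rule out early effects.

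What the defence does not supply is the correlation, the number of samples averaged, or a reason to expect the full effect in each of them.

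**Conclusion.** The >80% in Section 14.5 is unsupported and cannot be reproduced from the inputs given. If 4.9% is the SD of the within-person change, power is about 27% (n=8) or 20% (n=6) by t-test, and 23% or 13% by the planned Wilcoxon test. If 4.9% is a single-measurement SD, the claim needs an unstated correlation somewhere between 0.48 and 0.83 (n=8) or 0.66 and 0.89 (n=6), depending on whether ten or only one post-dose value is used. The CD8+ figure in the synopsis is not in conflict with this, but its basis needs stating too, because 1.6% as an SD of change gives 91–98%.

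These results rest on two-sided 5%, normal data, compound symmetry and a full effect in every averaged sample. The mixed models might use the samples differently from a plain average, but they too need the missing correlation before a power can be stated.

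**What to change.** Delete the sentence claiming >80% power for a 2.7% CD4+ change. Replace it with the CD4+ change detectable at 80% power, and state with it:

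- alpha and sidedness;
- whether the SD is that of a level or of the within-person change;
- the assumed within-person correlation and its source;
- the visit, or the number of post-dose samples averaged;
- the test the figure refers to, and whether n is 8 or 6.

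If 4.9 proves to be the SD of the change, the entry would be about 5.7 points (n=8) or 7.0 (n=6) for a paired t-test, or about 6.1 (1.25 × SD) or 8.8 (1.80 × SD) for the planned Wilcoxon test, two-sided 5%. If it is a single-measurement SD, the figure should come from the step 3 formula with a justified correlation.

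Give the CD4+ and CD8+ calculations on the same basis in both the synopsis and 14.5, each with its own SD.

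The cost is wording only. On the direct paired reading the stated power becomes less favourable; no participants, visits or samples are added.

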15 DATA COLLECTION, RETENTION AND MONITORING

15.1 Data Collection Instruments

The Investigator will prepare and maintain adequate and accurate source documents designed to record all observations and other pertinent data for each participant treated with the study drug.

Case report forms (CRFs) will be provided for each participant. Study personnel will enter data from source documents corresponding to a participant's visit into the protocol-specific paper CRF when the information corresponding to that visit is available. Participants will not be identified by name in the study database or on any study documents to be collected by the study investigators, but will be identified by a four-digit patient identification number (PID). If a correction is made on a CRF, the study staff member will line through the incorrect data, write in the correct data and initial and date the change.

The Principal Investigator is responsible for all information collected on participants enrolled in this study. All data collected during the course of this study must be reviewed and verified for completeness and accuracy by the Principal Investigator. A copy of the CRF will remain at the study site at the completion of the study.

15.2 Data Management Procedures

All data for our proposed study will be managed by the UCSF Data Coordinating Center, which is housed in the Department of Epidemiology and Biostatistics. This center currently serves 25 multicenter cohort and randomized trials throughout the world. Data management for this study will be directed by [name], who has worked on similar studies for the past five years.

The UCSF Department of Epidemiology and Biostatistics complies with federal, state, University, and campus electronic information security requirements through a combination of physical, technical, procedural, and management controls. At the procedural level, all Coordinating Center (CC) personnel sign a confidentiality agreement

and undergo security awareness training for HIPAA and the handling of sensitive data. All employees of the University of California, San Francisco were required to obtain Security Awareness Training and implement appropriate security measures. New employees who use computers must take this training. Remote users of the data also receive training from the Data Management Group prior to gaining access to data systems.

15.3 Data Quality Control and Reporting

After data have been entered into the study database, a system of computerized data validation checks will be implemented and applied to the database on a regular basis. Query reports (Data Clarification Requests) pertaining to data omissions and discrepancies will be forwarded to the Investigators and study monitors for resolution. The study database will be updated in accordance with the resolved queries. All changes to the study database will be documented.

15.4 Archival of Data

The database is safeguarded against unauthorized access by established security procedures; appropriate backup copies of the database and related software files will be maintained. Databases are backed up by the database administrator in conjunction with any updates or changes to the database.

The network at UCSF CC is privately maintained, hardware firewalled and none of the workstations or database servers can be directly addressed from outside the Local Area Network. Website communications are encrypted using an SSL certificate. Network OS is Windows Active Directory. Remote access is via SSL-VPN. A network administrator and server administrators support the network and servers and the Data Systems Services Group (developers/database administrators) support the database and web applications. The support team is paged 24/7 when servers or critical data center equipment experiences issues.

All study data is housed at the UCSF CC in a secure server room. The building is locked outside of normal business hours. All system servers are located in a limited access suite fitted with an Access Control System. Within the locked suite is a locked server room fitted with an additional secure door. Only critical Information Systems staff possesses the access code required to enter the room. All who enter the system server room must sign a server room access log in accordance with UCSF CC IT Security SOPs.

Study database access is controlled via two-factor password security. Development workstation access is controlled via Microsoft logon. Once a workstation is accessible, access to the study data on the SQL server via any development application requires appropriate logon-specific permission assigned in SQL Security Manager. Communication between study servers and client machines on the UCSF network are encrypted using an SSL certificate. All servers are protected from viruses by McAfee VirusScan. This software automatically checks for virus signature file updates from a McAfee FTP site once an hour, and if necessary directly updates itself. All anti-virus software is monitored and network personnel notified in the event that the software stops functioning on a given server.

All study data are stored on SQL servers managed by the UCSF Coordinating Center. All servers are housed in a secure server room.

Web site access: The study web sites are protected by two hardware-based firewalls to shape incoming and outgoing traffic. Access to the study management web site is restricted to approved personnel only. Approved personnel gain access to the system using a multi-layered authentication scheme. A log of all personnel with level of access is kept and updated regularly. Once a clinic site user accesses the system they are only permitted to view data received from their site, with the exception of official aggregate reports. Users are not permitted to view or alter another clinic's data.

Data transmission from web server to client: The UCSF CC currently utilizes Secure Socket Layer (SSL) protocol which protects all data transmission sent over the Internet between the CC IIS Web Server and every client machine which accesses our study web sites.

System Backup

Back-ups: All department workstations and servers are automatically backed-up every night. Back-up systems are monitored daily.

Failover Site: As part of the nightly database maintenance procedures, all SQL databases are backed up to a "failover" site at our co-location facility. This site has copies of the study databases as well as all associated systems required to carry on a study in the event of a disaster at the primary location.

Off-site Storage: Network back-ups are written to tape and sent to an off-site vendor every two weeks, with tapes being rotated every two months.

Recovery/File Restores: If important files or data from the network are accidentally deleted, the IT staff can locate the items and restore data within an hour in most cases.

15.5 Availability and Retention of Investigational Records

The Investigator must make study data accessible to the monitor, IRB, and Regulatory Agency (e.g., FDA) inspectors upon request. A file for each participant must be maintained that includes the signed Informed Consent, HIPAA Authorization and copies of all source documentation related to that participant. The Investigator must ensure the reliability and availability of source documents from which the information on the CRF was derived.

All study documents (patient files, signed informed consent forms, copies of CRFs, Study File Notebook, etc.) must be kept secured for a period of two years following marketing of the investigational product or for two years after centers have been notified that the IND has been discontinued.

15.6 Participant Confidentiality

In order to maintain participant confidentiality, only a site number, participant number and participant initials will identify all study participants on CRFs and other documentation submitted to the Sponsor.

16 ADMINISTRATIVE, ETHICAL, REGULATORY CONSIDERATIONS

The study will be conducted according to the Declaration of Helsinki, Protection of Human Volunteers (21 CFR 50), Institutional Review Boards (21 CFR 56), and Obligations of Clinical Investigators (21 CFR 312).

To maintain confidentiality, all laboratory specimens, evaluation forms, reports and other records will be identified by a coded number and initials only. All study records will be kept in a locked file cabinet and code sheets linking a patient's name to a patient identification number will be stored separately in another locked file cabinet. Clinical information will not be released without written permission of the participant, except as necessary for monitoring by the FDA. The Investigator must also comply with all applicable privacy regulations (e.g., Health Insurance Portability and Accountability Act of 1996, EU Data Protection Directive 95/46/EC).

16.1 Protocol Amendments

Any amendment to the protocol will be written by the study investigators. Protocol amendments cannot be implemented without prior written IRB approval except as necessary to eliminate immediate safety hazards to patients. A protocol amendment intended to eliminate an apparent immediate hazard to patients may be implemented immediately, provided the IRBs are notified within five working days.

